18.0 Confidentiality

A. Confidentiality of Study Data

Describe the local procedures for maintenance of confidentiality of study data and any records that will be reviewed for data collection.

18.1 A. Where and how will all data and records be stored? Include information about: password protection, encryption, physical controls, authorization of access, and separation of identifiers and data, as applicable. Include physical (e.g. paper) and electronic files.

Response: All patients' data records will be stored on password protected computers and or in locked cabinets within the research department. The research unit is locked after 5pm daily and all day on weekends. Identifiable patient information along with randomization information for each patient will be stored in locked cabinets in an locked archive room. This will only be accessible by

study coordinator and the PI. Electronic data will be stored on password protected computers as coded data based on randomization number eg R-12 without any patients identifiable information attached. These electronic files will only be accessible by authorized study personnel.

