4.0 Study Design

4.1 Describe and explain the study design (e.g. case-control, cross-sectional, ethnographic, experimental, interventional, longitudinal, observational).

Response:

This is a single center, prospective, double blind, randomized, placebo –controlled in a parallel design study. The study will be conducted at the Diabetes – Endocrinology Center of Western New York under the direction of [name], M.D, [name], MD and [name], PhD.

Ninety (90) T2DM patients with micro- or macroalbuminuria (45 each) will be enrolled and randomized into 2 groups to receive placebo or exenatide-extended release treatments for 1 year. The study groups and treatment arms of this study are:

1. T2DM with Microalbuminuria: 30 patients on Exenatide extended release and 15 patients on placebo for 1 year
2. T2DM with Macroalbuminuria: 30 patients on Exenatide extended release and 15 patients on placebo for 1 year

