19.0 Provisions to Monitor the Data to Ensure the Safety of Subjects

- N/A:** This study is not enrolling subjects, or is limited to records review procedures only. This section does not apply.

NOTE: Minimal risk studies may be required to monitor subject safety if the research procedures include procedures that present unique risks to subjects that require monitoring. Some examples include: exercising to exertion, or instruments that elicit suicidality or substance abuse behavior. In such cases, N/A is not an acceptable response.

19.1 Describe the plan to periodically evaluate the data collected regarding both harms and benefits to determine whether subjects remain safe.

Response: The principal investigator [name], PhD and co-investigators, [name] and [name] will review the data at the completion of all visits off each subject and every 3 months to assess the safety and any potential risks or benefits to the participants. Furthermore they will also assess other risks including the physical, psychological, social, legal and economic harm to these patients. The investigators listed above will carefully watch for any invasion of privacy and breach of confidentiality. The principal investigator will be sharing the results of safety analysis of the study with AZ and with the IRB. The study groups will remain blinded. If there are any safety concerns then co-investigator [name] who is not directly involved with the study participants will unblind the study groups on the discretion of principal investigator and tabulate and present unblinded data to the investigators for review. Based on review of the data presented, assessment of potential harm to the patients will be carried out to determine the best course of action. The IRB and sponsor will be informed of this potential harm along with the recommended course of action. Research subjects will be withdrawn from the study if risks are significant and/or

not manageable (see subject withdrawal section). The IRB will be kept well-informed at all times.

19.2 Describe what data are reviewed, including safety data, untoward events, and efficacy data.

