20.0 Withdrawal of Subjects

N/A: This study is not enrolling subjects. This section does not apply.

20.1 Describe anticipated circumstances under which subjects may be withdrawn from the research without their consent.

Response: The principal investigator of the study can remove a participant from the research study without their approval if for any reason he/she feels is appropriate, including

- i. Pregnancy
- ii. Developing conditions included in the exclusion criteria
- iii. Subjects decision to withdraw from the study
- iv. Severe side effects specific to study drugs
- v. Any medical condition that may place patient at risk of further complications
- vi. failure to take the medication as instructed, failure to keep your scheduled appointments,
- vii. cancellation of the study by the sponsor, or other administrative reasons.

20.2 Describe any procedures for orderly termination.

NOTE: Examples may include return of study drug, exit interview with clinician. Include whether additional follow up is recommended for safety reasons for physical or emotional health.

Response: If a subject withdraws from the research, the data collected to that point will be used toward the research finding. If applicable the subject will have to bring back any unused research drug and or device. If necessary, they will be asked to complete an end of study visit for their safety.

20.3 Describe procedures that will be followed when subjects withdraw from the research, including retention of already collected data, and partial withdrawal from procedures with continued data collection, as applicable.

Response: If a subject withdraws from the research, the data collected to that point will be used toward the research finding. If applicable the subject will have to bring back any unused research drug and or device. If necessary, they will be asked to complete an end of study visit for their safety.

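### Section 19.1 lets the PI have the study groups unblinded on any safety concern and shown to the trial's own investigators, without saying who stays blinded; Section 18.1 leaves the holder of the allocation list unstated

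*Combined protocol and SAP*

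**What the plan says.** Section 4.1 describes the trial as "single center, prospective, double blind, randomized", with placebo control. Section 19.1, the safety monitoring plan, states the default: "The study groups will remain blinded". It then gives the exception. On a safety concern, a co-investigator described as having no direct involvement with participants "will unblind the study groups on the discretion of principal investigator and tabulate and present unblinded data to the investigators for review". The investigators use that review to settle a course of action, which goes to the IRB and the sponsor.

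Under Section 20.1 the PI "can remove a participant from the research study without their approval if for any reason he/she feels is appropriate".

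Section 18.1, on confidentiality of study data, says: "Identifiable patient information along with randomization information for each patient will be stored in locked cabinets in an locked archive room". Access is restricted to the "study coordinator and the PI". The same answer continues: "Electronic data will be stored on password protected computers as coded data based on randomization number eg R-12".

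**The concern.** A double blind protects more than the reading of the endpoint. It also protects decisions that staff make during the year: which background drugs are changed, who is withdrawn, and which adverse events are recorded and how. Section 19.1 gives unblinded results to the people placed to influence those decisions. The trigger is undefined, the decision rests with the PI, and what is opened is the study groups rather than one patient's code.

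Withdrawal matters most for the primary comparison. Sections 20.2 and 20.3 use data only up to the point of withdrawal. If withdrawals, or changes in other treatment, came to depend on known arm, the later albuminuria values in the two arms would no longer be comparable.

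Section 18.1 raises a second question, who holds the treatment code. If the PI and coordinator hold it, the blind rests on their not looking. If they do not, the protocol should say who does.

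**Working it through.** There is no figure to reproduce. The check sets the sections side by side.

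**Unblinding rule**

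1. *Default.* Sections 4.1 and 19.1 agree that the trial is double blind and the groups stay blinded.
2. *Trigger.* Section 19.1 speaks of any safety concern and sets no threshold. Section 19.9 lists conditions for suspending the research but does not tie them to unblinding.
3. *Who decides.* The PI, by discretion.
4. *Who unblinds.* A co-investigator separate from participants. This is a genuine safeguard.
5. *Who sees the result.* The investigators. Section 19.6 makes the PI and co-investigators the three-monthly safety reviewers, and no independent committee is named. The safeguard in step 4 ends here.
6. *What they can then influence.* Section 20.1 gives the PI discretionary withdrawal, and Section 19.1 foresees withdrawals after such a review. Section 21.2 has the PI or sub-investigators review adverse events. Section 14.2 has the PI supervise the project, with weekly meetings on conduct, safety and analysis. Section 10.1 has other diabetes drugs reviewed and adjusted at study visits, without naming who does it.
7. *Afterwards.* No section says who remains blinded, at what level (group or patient), or until when. No single-patient code break is described.

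**Custody of the code**

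1. Section 18.1 does not define *randomization information*.
2. *Narrow reading.* It means the link from a person to a number such as R-12. That number is the subject code in Sections 18.1, 18.6 and 30.1. The unblinding step in Section 19.1 also fits a PI who does not already hold the arms.
3. *Broad reading.* It includes treatment arm. The same answer uses a narrower term, the randomization number, for the code, and nothing excludes the arm.
4. *Other holders.* Section 31.2 has the research nurse dispense study drug and says nothing about the list. Section 19.1 implies that the co-investigator can reach the code but does not make that person its holder.

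The text settles neither reading, and under both the holder of the allocation list is unnamed.

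**Endpoint**

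Section 10.1 (urinary measurements) has albuminuria assayed by an outside laboratory. The measurement itself is therefore little exposed to knowledge of arm.

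**The case against.** The best case for the plan has four parts.

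*Section 18.1 is about confidentiality, not code custody.* A locked file linking identity to study number, open to two people, is ordinary practice. This largely stands. A reader might infer that the PI and coordinator have standing access to the allocation of all 90 patients. The documents do not support that: the randomization number doubles as the subject code, and Section 19.1 keeps the groups blinded and uses a separate unblinder. What remains is an undefined term and an unnamed list holder.

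*The unblinding is conditional.* It may never happen, it serves patient safety, and the IRB and sponsor are informed. That is true, and the defect bites only if the rule is used. But the rule has no threshold and no provision for what follows.

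*Unblinding the groups and tabulating may mean group tables only.* That is a fair reading, and the text does not say that individual codes are handed over. Even so, tables labelled by arm would show investigators comparative results in a running trial, and patient-level listings are not ruled out.

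*Arm-dependent conduct is conjecture, and the endpoint comes from a laboratory.* Both points stand. The documents show an opportunity for bias and nothing more, and they do not name who adjusts background drugs or checks compliance. A reader might also take the planned 15% drop-out (0.15 × 90 = 13.5, or 13 to 14 patients) as the number exposed to arm-dependent decisions. That is unsupported: the 15% is a planning allowance without regard to cause, and Section 20.1 includes pregnancy, side effects and the patient's own choice among its reasons.

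**Conclusion.** The point holds as a gap in the unblinding rule, with a related ambiguity about custody of the code. If Section 19.1 is followed as written after a safety concern, the blind claimed in Section 4.1 is broken for the investigators mid-study, at least at group level, and nothing limits or ends that state. Section 18.1 needs clarifying, but it does not establish that anyone running the trial holds the allocation list.

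The risk runs through co-treatment, withdrawal and adverse event recording, not through the assay. Its size cannot be computed from the documents, and no number of affected patients should be claimed. The conclusion rests on reading the investigators in Section 19.1 as the trial's own PI and co-investigators, which Section 19.6 supports. It is worth acting on because the remedy is cheap.

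**What to change.** **Section 19.1.** State that the co-investigator with no direct participant involvement tabulates and reviews the unblinded data. Names are removed from the public text, so the sponsor should confirm that this person is not otherwise involved in study conduct, including as one of the three-monthly safety reviewers. The other investigators see group-level results under masked labels, as percentages, because denominators of 60 and 30 would identify the arms under 2:1 allocation. Percentages reduce this risk but do not remove it: 1/60 = 1.7% cannot arise from 30 patients, where one event is 1/30 = 3.3%, so very rare events need coarser display. Individual codes are opened only for a patient whose care requires it. State who stays blinded after such a review.

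**Section 18.1.** State that the file open to the PI and coordinator holds only the link between identity and randomization number, and that the allocation list is held by that co-investigator or by the drug supplier.

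**Cost.** Protocol wording only, using a person the plan already provides for if independence is confirmed, or the supplier for the list. Visits, endpoints and sample size do not change. The downside is one extra step when a code must be broken.

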18.2 A. How long will the data be stored?

Response: Data and specimens storage has no expiration date and will be stored for a minimum of 7 years. The researchers may continue to rely on this for future use in research study

18.3 A. Who will have access to the data?

Response: Those physicians, nurses, and laboratory staff that are on all documentation for the study will have access to the data.

18.4 A. Who is responsible for receipt or transmission of the data?

Response: Those physicians, nurses, and laboratory staff that are on all documentation for the study will have access to the data and can handle transfer of data.

18.5 A. How will the data be transported?

Response: All data are stored at one location and is not transported unless it is being archived. At that point files will be transferred to Iron Mountain for storage and archiving.

B. Confidentiality of Study Specimens

Describe the local procedures for maintenance of confidentiality of study specimens.

- N/A:** No specimens will be collected or analyzed in this research.
(Skip to Section 19.0)

18.6 B. Where and how will all specimens be stored? Include information about: physical controls, authorization of access, and labeling of specimens, as applicable.

Response: The specimens will be stored in the CRC laboratory located at [name] and at the CTRC located in [name]. Samples will be stored in a locked -80° C freezers. Ultimately, all specimens will be transported to CTRC location for banking. Specimens will be labeled as a coded sample, using the patient's randomization number (e.g. R-12), visit time and number and sample type. Specimens will not be stored with any patient identifiable information which is kept in locked cabinets in the CRC at [name].

18.7 B. How long will the specimens be stored?

Response: Specimens storage has no expiration date and will be stored for a minimum of 7 years. The researchers may continue to rely on this for future use in research studies.

18.8 B. Who will have access to the specimens?

Response: Those physicians, nurses, and laboratory staff that are on all documentation for the study will have access to the specimens.

18.9 B. Who is responsible for receipt or transmission of the specimens?

Response: Those physicians, nurses, and laboratory staff that are on all documentation for the study will have access to the specimens and can handle transfer of samples.

18.10 B. How will the specimens be transported?

Response: Fresh samples collected for screening and safety will be transported by Quest Diagnostics courier at ambient temperature and according to Quest Diagnostics instructions. Frozen samples that are transported will be done so using dry ice in a properly labeled Styrofoam container by the laboratory technician.

19.0 Provisions to Monitor the Data to Ensure the Safety of Subjects

- N/A:** This study is not enrolling subjects, or is limited to records review procedures only. This section does not apply.

NOTE: Minimal risk studies may be required to monitor subject safety if the research procedures include procedures that present unique risks to subjects that require monitoring. Some examples include: exercising to exertion, or instruments that elicit suicidality or substance abuse behavior. In such cases, N/A is not an acceptable response.

19.1 Describe the plan to periodically evaluate the data collected regarding both harms and benefits to determine whether subjects remain safe.

Response: The principal investigator [name], PhD and co-investigators, [name] and [name] will review the data at the completion of all visits off each subject and every 3 months to assess the safety and any potential risks or benefits to the participants. Furthermore they will also assess other risks including the physical, psychological, social, legal and economic harm to these patients. The investigators listed above will carefully watch for any invasion of privacy and breach of confidentiality. The principal investigator will be sharing the results of safety analysis of the study with AZ and with the IRB. The study groups will remain blinded. If there are any safety concerns then co-investigator [name] who is not directly involved with the study participants will unblind the study groups on the discretion of principal investigator and tabulate and present unblinded data to the investigators for review. Based on review of the data presented, assessment of potential harm to the patients will be carried out to determine the best course of action. The IRB and sponsor will be informed of this potential harm along with the recommended course of action. Research subjects will be withdrawn from the study if risks are significant and/or

not manageable (see subject withdrawal section). The IRB will be kept well-informed at all times.

19.2 Describe what data are reviewed, including safety data, untoward events, and efficacy data.

Response Safety data (vitals, CBC, CMP, urinary markers) will be collected at screening, during and at end of the study. Injection site reactions and hypoglycemia data will be monitored and collected at every visit. Physical examination will be performed at 26 and 52 weeks visits and safety assessments performed. Pregnancy results and contraceptive adherence plan (if applicable) will be reviewed at screening, 16 and 39 and 52 weeks.

19.3 Describe any safety endpoints.

Response: N/A.

19.4 Describe how the safety information will be collected (e.g., with case report forms, at study visits, by telephone calls with participants).

Response: The safety information will be collected at the time of the participants visit, and or during telephone calls with the participant using source documents.

19.5 Describe the frequency of safety data collection.

Response: The data collection will be done at all study visits which will be at intervals of either one or two weeks depending on the number of study visit. The patients, however, will be asked to report any adverse event or safety related information via phone as soon as it occurs and it will be reviewed the same day.

19.6 Describe who will review the safety data.

Response: The principal investigator [name], PhD and co-investigators, [name] and [name] will review the data at the completion of all visits by each subject and every 3 months to assess the safety and any potential risks to the participants.

19.7 Describe the frequency or periodicity of review of cumulative safety data.

Response: Every 3 months, [name], [name] and [name] will assess the safety and any potential risks to the participants. Safety data (vitals, CBC, CMP, urinary markers) will be collected at screening, during and at end of the study. Injection site reactions and hypoglycemia data will be monitored and collected at every visit. Physical examination will be performed at 26 and 52 weeks visits and safety assessments performed. Pregnancy (if applicable) will be tested at screening, 16 and 39 and 52 weeks. Oral anti-hyperglycemic agents and/or insulin dose titration will be done to avoid hypoglycemia. Phone calls will be made for safety and compliance follow-up at least 6 time during the study. The patients, however, will be instructed to report any adverse event or safety related information via phone as soon as it occurs. All safety data will be reviewed by the PI or sub-investigators within 1-2 days of collection.

19.8 Describe the statistical tests for analyzing the safety data to determine whether harm is occurring.

Response: The statistical analysis will be carried out using the student t-test or Wilcoxon's test for paired data.

19.9 Describe any conditions that trigger an immediate suspension of the research.

Response:

1. New safety information becoming available concerning the safety of study drugs.
2. Termination of funding.
3. Withdrawal of study drug by FDA
4. Significant increase in risks (beyond expected risks) based in review of safety data.

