The secondary end points include the comparison of the changes in albuminuria based on baseline albuminuria category (micro or macro), creatinine clearance, Cystatin C, TGF β , type I and IV collagen, CTGF, and fibronectin levels, the expression of SMAD3, SMAD4, NQO-1, GST-1P and HO-1, Nrf-2/keap-1 system activation between the Exenatide extended release and placebo groups and across albuminuria categories.

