10.0 Procedures Involved

10.1 Provide a description of **all research procedures or activities** being performed and when they are performed once a subject is screened and determined to be eligible. Provide as much detail as possible.

NOTE: This should serve as a blueprint for your study and include enough detail so that another investigator could pick up your protocol and replicate the research. For studies that have multiple or complex visits or procedures, consider the addition of a schedule of events table in in your response.

Response:

Visit 1 (week 0):

Qualifying subjects will be asked to come for the visit in a fasting state (10-12 hr fasting), vitals will be done and safety labs for CBC, CMP, HbA1C, kidney function tests will be drawn and 24hr urine will be collected. Blood samples (30ml) will be collected for research endpoints. Training on administrating study drug and information about side effects and how to report any adverse events will be discussed with patients. One of the treatment arms will be administered to the patient (placebo or Exenatide extended release in a randomized fashion) and enough drug supply for 13+2 weeks will be dispensed. Other diabetes medications will be reviewed and any standard of care adjustments will be made. A 24hr urine collection container will be dispensed and patients will be instructed to come back after 13 weeks.

Visits 2, 3 and 4 (Weeks 13, 26 and 39):

Patients will come to this visit in the fasting state. Physical exam (only on visit 3) and vitals will be performed, safety labs for CBC, CMP, HbA1c, kidney function tests will be drawn and 24hr urine collected. Blood samples (30ml) will be collected for research endpoints. Other diabetes medications will be reviewed and any standard of care adjustments will be made. Study medication use compliance will be assessed and drug supply for 13+2 weeks will be dispensed. A 24hr urine collection container will be dispensed and patients will be instructed to come back after 13 weeks.

Visit 5 (Week 52): Patients will come to this visit in the fasting state. Physical exam and vitals will be performed, safety labs for CBC, CMP, HbA1c, kidney function tests will be drawn and 24hr urine collected. Blood samples (30ml) will be collected for research endpoints. Other diabetes medications will be reviewed and any standard of care adjustments will be made. Patient will be discharged from the study after the final safety phone call at week 56.

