17.0 Data Management and Analysis

17.1 Describe the data analysis plan, including any statistical procedures. This section applies to both quantitative and qualitative analysis.

Response: **DATA ANALYSIS**

This is a prospective study to evaluate effect of Exenatide extended release treatment for 1 year on albuminuria levels in T2DM patients with micro- and macroalbuminuria compared to placebo. The similarities in baseline values between the study groups will be compared using appropriate parametric tests. Transformations of the data on order to meet statistical assumptions may be considered. All statistical analysis will be carried out using SPSS software (SPSS Inc, Chicago, Illinois) based on intention to treat principle. Data will be presented as mean±standard error. The primary endpoint of the study is the change from baseline in albuminuria level at weeks 12, 26, 39 and 56 following Exenatide extended release and placebo treatments. Fasting samples collected at weeks 0, 12, 26, 39 and 56 will be used for this assessment with values at week 0 considered as baseline. Changes from baselines from both drugs arms will be compared to those from the placebo arms in both the micro and macroalbuminuria groups. The statistical analysis will be done using mixed model for repeated measurement (MMRM) analysis with assigned α value of 0.05. Our preliminary data on retrospective analysis of the difference in albuminuria following GLP-1RA treatment for 2.5 yrs in T2DM patients with micro and macroalbuminuria show regression of albuminuria (UACR) by approximately 55mg/mg and 500mg/g (about 50% reduction), respectively.

The secondary end points include the comparison of the changes in albuminuria based on baseline albuminuria category (micro or macro), creatinine clearance, Cystatin C, TGF β , type I and IV collagen, CTGF, and fibronectin levels, the expression of SMAD3, SMAD4, NQO-1, GST-1P and HO-1, Nrf-2/keap-1 system activation between the Exenatide extended release and placebo groups and across albuminuria categories

17.2 If applicable, provide a power analysis.

NOTE: This may not apply to certain types of studies, including chart/records reviews, survey studies, or observational studies. This question is asked to elicit whether the investigator has an adequate sample size to achieve the study objectives and justify a conclusion.

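### The only safety tests named (19.8) are for paired data, and no final exenatide-versus-placebo analysis of vitals, blood counts, non-renal chemistry, hypoglycemia or injection-site reactions is stated

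*Combined protocol and SAP*

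**What the plan says.** Section 19.8 asks which statistical tests will show whether patients are being harmed. The whole answer is: "The statistical analysis will be carried out using the student t-test or Wilcoxon's test for paired data".

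Section 4.1 describes a double-blind, randomised trial, "controlled in a parallel design study". Section 17.2 gives 60 patients on exenatide and 30 on placebo.

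The safety data in 19.2 are vitals, CBC, CMP and urinary markers, and also events: "Injection site reactions and hypoglycemia data will be monitored and collected at every visit". Section 19.3 declares safety endpoints not applicable.

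On monitoring, 19.1 says "The study groups will remain blinded". If a safety concern arises, and at the principal investigator's discretion, a co-investigator not directly involved with participants will unblind the groups and "tabulate and present unblinded data to the investigators for review".

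Section 17.1 gives an MMRM for albuminuria and then the secondary comparisons: "The secondary end points include the comparison of the changes in albuminuria", followed by renal, fibrosis and oxidative-stress markers. Section 2.1 carries the same list, compared "between the Exenatide extended release and placebo groups and across albuminuria categories".

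**The concern.** A paired test compares each patient with that patient's own baseline. The placebo arm is there to show what would have happened without the drug, and a paired test leaves it out. If blood pressure, a blood count or a liver enzyme moves over a year in everyone, a paired test can signal harm that the drug did not cause. If a shared improvement offsets a drug-related worsening, it can miss harm that the drug did cause.

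Some shared change is possible here. At each visit, Section 10.1 says, "Other diabetes medications will be reviewed and any standard of care adjustments will be made". Review is universal and adjustment is as needed, so the resulting change may also differ between arms.

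The named tests also do not suit hypoglycemia and injection-site reactions. These are events for which no baseline value is described, so there is no natural pair. Section 31.1 shows that placebo is also an injected product, so injection-site reactions can occur in both arms and need a comparison between them.

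At stake is whether the final report must use the control group to attribute these safety findings to exenatide. As written, it need not.

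**Working it through.** **1. Is a between-arm safety analysis stated anywhere?**

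| Section | Content | Between-arm analysis of vitals, CBC, non-renal chemistry, hypoglycemia or injection-site reactions? |
|---|---|---|
| 2.1, 17.1 | MMRM for albuminuria; secondary comparisons of creatinine clearance, cystatin C, fibrosis and oxidative-stress markers | No. Some renal markers are covered, hence the restriction to non-renal chemistry |
| 17.1 | General sentence on software and intention to treat | No safety comparison named |
| 19.1 | Unblinded tabulation on a concern, at discretion; safety results go to the supporting company and the IRB | Conditional; no estimate, test or final analysis |
| 19.3 | Safety endpoints not applicable | No |
| 19.8 | Paired-data tests | No |
| 19.9 | Suspension conditions, including a rise in risk judged from review of safety data | Not tied to any test |

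The wording of 19.8 allows a second reading, in which the paired qualifier attaches only to the Wilcoxon test. The t-test is then unspecified, and a comparison of exenatide with placebo is still not stated.

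**2. What each test estimates.** Let s be the change shared by both arms and δ the extra change due to exenatide, both in units of the SD of individual change. With 60 and 30 patients:

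- pooled mean change = (60(s + δ) + 30s)/90 = s + (2/3)δ
- exenatide mean minus placebo mean = (s + δ) − s = δ

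The pooled paired test therefore examines s + (2/3)δ. Only the between-arm contrast isolates δ.

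**3. Size, as an illustration.** The plan gives no figure for safety power or drift, so there is none to reproduce. Inputs from the plan are n = 60 + 30 = 90 and 15% drop-out (17.2). Inputs assumed are normal data, two-sided 5% level, δ = 0, and s = 0.1, 0.2 or 0.3. The paired t-test has noncentrality s√n on n − 1 degrees of freedom.

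| s (assumed) | s√90 | Pooled paired test significant, n=90 | n=77 (90 × 0.85 = 76.5, rounded up) | Between-arm test, 60 vs 30 |
|---|---|---|---|---|
| 0.1 | 0.95 | 15.5% | 13.9% | 5.0% |
| 0.2 | 1.90 | 46.7% | 41.0% | 5.0% |
| 0.3 | 2.85 | 80.4% | 73.9% | 5.0% |

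The first two percentage columns come from the noncentral t distribution. The last comes from 100,000 simulated trials at each drift.

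**4. Precision of a between-arm event comparison.** The Wald 95% half-width is 1.96 × √(p₁(1−p₁)/60 + p₀(1−p₀)/30), with assumed event rates:

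- 20% vs 10%: 1.96 × √(0.00267 + 0.00300) = 0.148
- 30% vs 10%: 1.96 × √(0.00350 + 0.00300) = 0.158

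That is about 15 to 16 percentage points. An exact interval would differ.

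**The case against.** The strongest reply is that 19.8 belongs to a section on monitoring during the trial. With the groups blinded, monitors cannot compare arms without breaking the blind, so a paired test on pooled data is what is open to them. This stands, and it is why the paired test can be kept as screening. It does not supply a final analysis: if 19.8 covers monitoring only, the plan states no end-of-trial analysis of these safety variables at all.

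A second reply is that 19.1 already allows arms to be compared when there is a concern, and that adverse events are reviewed within 24 hours of reporting (21.2). Both are real safeguards. The first is conditional and discretionary, and the second judges individual cases; neither is a planned comparison of arms.

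A third reply is that the percentages rest on assumed drift. That is correct. They show how the test behaves and do not predict this trial's results.

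A reader might infer more than the documents support:

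- **That the team intends to omit a between-arm safety table.** The plan is silent; it does not say that none will be made.
- **That every patient's diabetes medication changes at every visit, giving an identical drift in both arms.** Section 10.1 provides for review at every visit and adjustment only where needed.
- **That paired tests will be run within the exenatide arm alone.** No section describes this, and routine blinded review would not permit it.
- **That a paired p-value could suspend the trial.** Section 19.9 ties suspension to no test.

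**Conclusion.** The point holds. The only stated safety method cannot attribute harm to exenatide and does not fit event data, and no section states a final exenatide-versus-placebo analysis of vitals, CBC, non-renal chemistry, hypoglycemia or injection-site reactions. This goes beyond missing detail, because the method that is stated would mislead if taken as evidence of a drug effect.

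Severity is minor to moderate. No stated suspension rule, primary analysis or sample size depends on it. The conclusion rests on reading the sections together and on the algebra of step 2. The illustrated range of 16% to 80% against 5% depends wholly on an assumed shared drift of 0.1 to 0.3 SD with no drug effect.

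**What to change.** (a) In 19.8, state that paired tests on blinded pooled data are screening only and cannot attribute a change to exenatide. Leave the 19.1 blinding and unblinding process as it is.

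(b) In 17.1, with a cross-reference from 19.8, add a final between-arm safety summary labelled as descriptive:

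- Vitals and laboratory values: exenatide-minus-placebo difference in change from baseline with 95% CI, adjusted for the baseline value and, preferably, the albuminuria stratum.
- Hypoglycemia, injection-site reactions and other adverse events: number of patients with each event in each arm, with the risk difference and 95% CI.

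The cost is one sentence, one paragraph and slightly more analysis work at the end. The data are already collected, so no extra visits or staff are needed. The drawback is low precision with 60 against 30 patients (step 4), so a wide interval should not be read as evidence of no harm.
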